PD	Progressive Disease
PD-1	Programmed Death-1
PFS	Progression Free Survival
PO (or p.o.)	Per os/by mouth/orally
PR	Partial Response
RCC	Renal Cell Carcinoma
RECIST	Response Evaluation Criteria in Solid Tumors
SAE	Serious Adverse Event
SD	Stable Disease
SGOT	Serum Glutamic Oxaloacetic Transaminase

SJS	Stevens-Johnson Syndrome
SPGT	Serum Glutamic Pyruvic Transaminase
TEN	Toxic Epidermal Necrolysis
TIL	Tumor Infiltrating Lymphocyte
TMZ	Temozolomide
TNBC	Triple Negative Breast Cancer
WBC	White Blood Cells

NU Study Number: NU 16MH03
BMS Study Number: CA 209-783
Abbvie Study Number: A15-831

STUDY SCHEMA

NU Study Number: NU 16MH03
BMS Study Number: CA 209-783
Abbvie Study Number: A15-831

STUDY SUMMARY

Title	Phase I/IB study of nivolumab and veliparib in patients with advanced solid tumors and lymphoma with and without mutations in selected DNA repair genes
Version	3/3/2020 (Amendment 7)
Study Design	Phase I/IB
Study Center	Northwestern University

NU Study Number: NU 16MH03
BMS Study Number: CA 209-783
Abbvie Study Number: A15-831

	
Primary Objectives:
 
A. To Identify the maximum tolerated dose (MTD) for combination treatment of nivolumab and veliparib in patients with advanced solid tumors and lymphoma with and without mutations in selected DNA repair genes.
 
Secondary Objectives:
 
A. To evaluate the toxicities and tolerability of nivolumab and veliparib in the study population.
 
B. To evaluate the efficacy of veliparib and nivolumab measured by overall response rate (ORR), clinical benefit rate (CBR), and progression free survival (PFS) using RECIST v1.1, Lugano classification, and irRECIST.
 
For the preliminary efficacy analysis, ORR will be computed at the first imaging (8 weeks). Preliminary efficacy will be evaluated by RECISTv 1.1. As exploratory analysis, irRECIST will be used to obtain preliminary efficacy as well. All ORR will use the first imaging time point whether RECIST or irRECIST.
 
C. To evaluate Overall Survival (OS) at 3 years from the start of treatment.
 
D. To evaluate the proportion of patients alive and progression free at 24 weeks in this population.
 
Exploratory Objectives:
 
A. Biomarker tests will be performed at baseline using fresh tissue (or archived if a fresh biopsy is not feasible), as well as from blood samples at Cycle 1 Day 1, Cycle 3 Day 1, and the End of Treatment visit. To evaluate if any of the following predict response to veliparib in combination with nivolumab:
 
• Tissue PD-L1 protein expression• Immune cell infiltration markers 
B. To demonstrate the pharmacodynamic effects of veliparib and nivolumab on biomarkers including PD-L1, TILs, T cell subpopulations, and T cell receptor genotype.

--	---

NU Study Number: NU 16MH03

BMS Study Number: CA 209-783

Abbvie Study Number: A15-831

Sample size	
The initial study design was to accrue a total of up to 50 patients for 48 evaluable) to the study in two phases: dose escalation and dose expansion. The original design anticipated a total of 6-18 patients with advanced solid tumors or lymphoma in the dose escalation phase; 9 patients were enrolled, including 3 at lowest dose and 6 that were treated at the MTD of 400 mg BID. It is still planned for 6 patients with advanced solid tumors and lymphoma with mutations in selected DNA repair genes to be enrolled into the expansion cohort to receive the maximum tolerated dose of veliparib in combination with nivolumab. However, due to funding issues, the study will perform an early analysis of preliminary efficacy after the next 6 patients are enrolled in the expansion cohort, all with the genetic mutation. Of the 6 patients already at MTD, 4 have the genetic mutation. No responses were observed in any patient at MTD. Total number of patients at the end of adding 6 more patients with mutation will be $4+6=10$. The study will be considered a “success” if the lower exact 90% confidence limit is $> 10\%$, i.e. when 3 or more successes are observed. . According to the modified plan for the current trial, the study will be closed after the 6 additional patients will have been recruited.”

--------------------	---

NU Study Number: NU 16MH03
BMS Study Number: CA 209-783
Abbvie Study Number: A15-831


Diagnosis & Key Eligibility Criteria
	
Key Inclusion Criteria:
 
1. Patients must have a histologically documented (either primary or metastatic site) diagnosis of metastatic or advanced solid cancer (stage IV or unresectable) or aggressive lymphoma. NOTE: The following histologies will be excluded given known response to PD-1/PD-L1 inhibitor monotherapy; non-small cell lung cancer, squamous cell carcinoma of head and neck, melanoma, renal cell carcinoma, bladder cancer, Hodgkin's lymphoma, Merkel cell carcinoma, and MSI-H colorectal cancer.2. All patients must have received at least one line of systemic treatment.3. Patients who progressed on single agent PD-1/PD-L1 inhibitors are allowed.4. Patients must be ECOG performance status of 2 or less and have normal organ function.5. For expansion cohort, patients should have alterations in selected DNA repair genes in their tumors, as listed in 3.1.6. Please note: This eligibility criteria is also applicable for patients enrolled for the preliminary expansion cohort to conduct preliminary efficacy analysis. 
Key Exclusion criteria:
 
1. Patients who have had chemotherapy or radiotherapy \leq 14 days prior to entering the study are not eligible.2. Patients may not have received systemic chemotherapy \leq 28 days prior to registration.3. Patients are not eligible who have had major surgery \leq 14 days of registration.4. Patients are not eligible who have received prior PARP inhibitors (including but not limited to veliparib, talazoparib, rucaparib, and olaparib).5. Patients are not eligible who have received prior immunotherapy including interleukin-2 and immune checkpoint antagonists and/or agonists (including but not limited to PD-1, PD-L1, CD137, or OX40). NOTE: Single agent anti-CTLA4 monoclonal antibody treatments are permitted. Cancer vaccine therapies are permitted.6. Patients are not eligible who have had a prior allogeneic stem cell transplant. NOTE: Autologous stem cell transplant is acceptable. Patients with autoimmune diseases are excluded.
--	--

NU Study Number: NU 16MH03
BMS Study Number: CA 209-783
Abbvie Study Number: A15-831


Treatment Plan
	
Patients will be treated using a dose escalation plan based on a 3+3 design. The starting dosing for veliparib will be 300 mg PO twice daily, and treatment will begin as monotherapy during a 7-day induction period. Patients in Phase Ib will be treated at the MTD.
 
Nivolumab combination therapy will begin Cycle 1 Day 1 as follows: Cycle 1-4: 240 mg IV every 14 days (Day 1 & 15) Cycle 5+: 480mg IV every 28 days (Day 1 of each cycle).
 
Combination treatment will continue until disease progression unacceptable toxicity, or withdrawal of consent.
 
This treatment plan is applicable for patients in both the dose escalation and dose expansion cohorts.

Statistical Methodology
	
The primary analysis will be based on toxicity and maximum tolerated dose. For all analyses, the intent-to-treat (ITT) population will be used to include all evaluable patients. Clinical benefit rate will be defined as stable disease (for ≥ 12 weeks) and complete or partial response by the Response Evaluation Criteria in Solid Tumors (RECIST). Lugano classification will be used for lymphomas. Maximum response prior to disease progression will be used. The overall response rate will be estimated by the proportion of overall response, and its 90% lower bound will be estimated using the exact binomial distribution. If this lower bound $> 10\%$ (ie. at least three responses are observed) the trial will be considered a success.
 
Additionally, we will evaluate overall response rate, separately for patients with and for those without genetic mutation entertained in this study, Early analysis of preliminary efficacy will be based on the patients with genetic mutation (n=10). Response is defined as complete or partial response using RECIST guidelines in a similar manner. We will also perform similar analyses using Immune Related RECIST (irRECIST). Duration of response, defined as the duration from the first documentation of clinical benefit to the first documented progressive disease or death of any cause, whichever occurs first, will also be analyzed. For patients alive and progression-free at the time of data cut off, duration of response will be censored as of the last tumor assessment date. Duration of response will only be evaluated for the subgroup of patients with a clinical benefit using the Kaplan-Meier method.

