4.2 Treatment Administration

Table 4.1: Dosing of Nivolumab and Veliparib

Drug	Dose	Route	Schedule
Nivolumab (Opdivo)	C1-4: 240mg C5+: 480mg	IV	Cycle 1-4: every 14 days Cycle 5+: every 28 days until progression of disease, intolerable toxicity, or withdrawal of consent
Veliparib	Phase I: Starting dose 300mg (see 4.3 for escalation) Phase Ib: MTD	PO	Twice a day about 12 hours apart starting 7 days before C1D1 (Induction monotherapy) continuing until progression of disease, intolerable toxicity, or withdrawal of consent

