4.10 Patient Replacement

If a patient is enrolled in the study but comes off study before cycle 1 day 1 of

treatment, the patient may be replaced.

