10.2 Sample Size and Accrual

The initial study has recruited 3 patients at the lower dose and 6 at the MTD. Of these 6 at the MTD, 4 have genetic mutation of interest, and 2 do not. The study will, due to lack of funding and other reasons recruit 6 more patients with genetic mutation of interest. The response rate will be computed separately for 4+6 = 10 patients with genetic mutation.

Dose Escalation Phase

The expected number of patients in the dose escalation phase will be in the range of 6 to

18 based on the 3+3 design.

Expansion Cohort

The initial study design was to accrue a total of up to 50 patients (for 48 evaluable) to the study in two phases: dose escalation and dose expansion. The original design anticipated a total of 6-18 patients with advanced solid tumors or lymphoma in the dose escalation phase; 9 patients were enrolled, including 6 that were treated at the MTD of 400 mg BID. Due to funding issues, the study will perform an early analysis of preliminary efficacy after the next 6 patients are enrolled in the expansion cohort.

As stated above, in **the modified plan for expansion cohort**, will accrue 6 new patients with genetic alteration for early preliminary efficacy assessment, which together with 4 previously treated patients with genetic mutation will provide total of 6+4=10 patients, with genetic mutation. ORR will be computed at the first imaging (8 weeks). Preliminary efficacy will be evaluated by RECISTv 1.1. As exploratory analysis, irRECIST will be used to obtain preliminary efficacy as well. All ORR will use the first imaging time point whether RECIST or irRECIST.

The study will be considered a success if the lower 90% exact confidence bound will be > 10% , i.e. if three or more successes out of n=10 are observed.

I According to the modified plan for the current trial, the study will be closed after the 6 additional patients will have been recruited.”

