10.3 Data Analyses Plans

The primary analysis will be on the intent-to-treat (ITT) population, including all evaluable patients. Clinical benefit rate will be defined as stable disease (for ≥ 12 weeks), complete or partial response by both the Response Evaluation Criteria in Solid Tumors (RECIST) and irRECIST or Lugano Criteria 2014. Maximum response prior to disease progression will be used. The overall response rate will be estimated by the proportion of overall response, and its 80% confidence..

Additionally, we will evaluate overall response rate, defined as complete or partial response using RECIST or Lugano Criteria 2014 guidelines in a similar manner. We will also perform similar analyses using Immune Related RECIST (irRECIST). Duration of response, defined as the duration from the first documentation of clinical benefit to the first documented progressive disease or death of any cause, whichever occurs first, will also be analyzed. For patients alive and progression-free at the time of data cut off, duration of response will be censored as of the last tumor assessment date. Duration of response will only be evaluated for the subgroup of patients with a clinical benefit using the Kaplan-Meier method.

PFS is defined as the time from treatment initiation to documented disease progression. OS is defined as the time from the start of treatment until death due to any cause. For patients alive at the time of data cut-off, PFS and OS will be censored as of the last tumor assessment date or known to be alive, respectively. The PFS and OS will be estimated using the Kaplan-Meier method. The number, frequency, and severity of adverse events (as defined by the NCI Common Terminology Criteria for Adverse Events or CTCAE version 4.03) will be recorded.

Baseline percent PDL1 expression, TILs (sTILs, iTILs, and their ratio), and changes in T

cell subpopulations will be used as a continuous variable to predict clinical benefit or overall response rates using appropriate statistical summaries. Cox proportional hazards regression will be used to compare how these biomarkers are associated with PFS and OS as well.

Changes in these biomarkers will also be analyzed to assess for pharmacodynamic effects of treatment. Continuous variables will be analyzed using either paired t-tests, signed rank tests or repeated measures analysis of variance.

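### The ORR success rule rests on two conflicting response definitions, and its set is labelled ITT but limited to undefined evaluable patients

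*Combined protocol and SAP*

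**What the plan says.** **When response is read.** Section 10.2 states "All ORR will use the first imaging time point whether RECIST or irRECIST". The same rule appears in the Study Summary objectives and in sections 1.9, 2.2.2, 4.3.3, 6.5.2 and 10.1, with the first scan at 8 weeks. The Statistical Methodology row of the Study Summary and section 10.3 say something else: "Maximum response prior to disease progression will be used". In both places this follows the definition of clinical benefit rate and comes directly before the sentence on estimating ORR. In the Study Summary the success criterion comes next.

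**Who is counted.** The Study Summary says "For all analyses, the intent-to-treat (ITT) population will be used to include all evaluable patients", and section 10.3 says "The primary analysis will be on the intent-to-treat (ITT) population, including all evaluable patients". Neither defines *evaluable*. The ORR denominator is given separately as a head count: "The response rate will be computed separately for 4+6 = 10 patients with genetic mutation" (section 10.2; also the Study Summary and sections 1.9 and 4.3.3).

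**Replacement.** Section 4.10 reads "If a patient is enrolled in the study but comes off study before cycle 1 day 1 of" treatment, that patient may be replaced. Table 4.1 has veliparib "starting 7 days before C1D1 (Induction monotherapy", so a replaced patient may already have taken study drug.

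**Success rule.** The exact 90% lower bound for ORR must exceed 10%, which the plan gives as three or more responses in ten. The Study Summary reports no responses so far in any patient at the MTD.

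**The concern.** The plan has one formal efficacy criterion, applied to ten patients, of whom four already count as non-responders. A response first seen on a later scan counts under one sentence and not under the other. With so few patients, one such response can decide whether the trial is declared a success, and nobody need be missing for that to happen.

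The second problem is the analysis set. An ITT set is not normally restricted to evaluable patients, and the plan's own usage separates the two ideas: the original design accrued 50 patients to obtain 48 evaluable. Read literally, the restriction allows a treated patient without a post-baseline scan to leave the denominator. Such patients are unlikely to be responders, so the error would run towards a higher ORR. What is at stake is mainly the reported rate and, through the response definition, the success label. Appendix E gives support for funding a larger trial as the reason for the modified plan, so that label may be used.

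**Working it through.** **Inputs.** N = 4 + 6 = 10 and 0 responses in the earlier four (Study Summary, Sample size); exact binomial 90% lower bound with a 10% threshold (Study Summary; section 10.2).

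**1. Reproduce the plan's figure.** The one-sided 90% Clopper-Pearson lower bound for x responses in N is the 0.10 quantile of Beta(x, N − x + 1). It exceeds 10% exactly when P(X ≥ x | N, 0.10) is below 0.10.

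- x = 3, N = 10: 1 − (0.3487 + 0.3874 + 0.1937) = 0.070, below 0.10. Bound 11.6%, pass.
- x = 2, N = 10: 1 − (0.3487 + 0.3874) = 0.264, above 0.10. Bound 5.5%, fail.

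The stated 3 of 10 reproduces. It does so only on the one-sided reading: the lower limit of a two-sided 90% interval at 3/10 is 8.7%, and four responses would be needed. The 80% level mentioned in section 10.3 gives the same lower limit as a one-sided 90% bound if it is a two-sided interval, so it is not a further conflict.

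**2. Response definition.** The earlier four contribute 0, so three of the six new patients must respond. Maximum response before progression includes any response seen at week 8, so its count can only equal or exceed the first-imaging count. Suppose three new patients respond, one of them first seen after week 8:

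| Reading | Responses | Lower bound | Decision |
|---|---|---|---|
| Maximum response | 3/10 | 11.6% | pass |
| First imaging | 2/10 | 5.5% | fail |

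**3. Effect of the denominator on the decision.** For a fixed number of responses the bound falls as N rises, so only the end points matter.

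| x/N | Lower bound | Exceeds 10%? |
|---|---|---|
| 2/5 | 11.2% | yes |
| 2/6 | 9.3% | no |
| 3/6 | 20.1% | yes |
| 3/11 | 10.5% | yes |
| 3/12 | 9.6% | no |
| 4/12 | 15.4% | yes |

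Two responses fail at every N of 6 or more, and three pass at every N up to 11. The cut-off is therefore three throughout N = 6 to 11. It falls to two only if at least five of the ten patients are left out (N of 5 or fewer). It rises to four only if two or more replaced patients are kept in addition to the ten (N = 12).

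**4. Effect on the reported rate.** Take three responses and one dosed non-responder replaced under section 4.10. Omitting that patient gives 3/10 = 30%; keeping the patient gives 3/11 = 27.3%, a difference of 2.7 percentage points. Both values pass.

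**5. Patients without a week-8 scan.** Table 5 schedules imaging at the End of Treatment visit, about 30 days after the last dose. For an early stopper that scan can fall before week 8. No section says whether it is then the first imaging, or how a patient with no post-baseline scan is counted for ORR.

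**The case against.** **The first-imaging rule should govern.** It is explicit, appears in seven places, and according to Appendix E was added by Amendment 5 for this analysis. The maximum-response sentence follows the clinical benefit definition, and the next paragraph introduces ORR as an additional evaluation, which suggests that the earlier text concerns clinical benefit. This is a reasonable account of the intention. It does not remove the conflict: the sentence carries no such limit, the next sentence estimates ORR, and in the Study Summary the success criterion stands in the same paragraph.

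**The denominator is already fixed at ten.** The head count is specific and the evaluable wording is general; they part only if a mutation-positive patient turns out not to be evaluable. That is correct, and it limits the point.

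**Early stoppers should usually have a scan.** Table 5 supports this. What is missing is the counting rule. A reader might infer that unscanned patients will be dropped; no section says so, only that the wording permits it.

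**Replacement occurs before any nivolumab.** The efficacy objective concerns the combination, so a denominator of patients who received both drugs is defensible. This stands. A reader might infer that the plan requires every dosed patient to be counted, but the documents do not settle it.

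**A stronger inference to avoid.** A reader might conclude that the undefined set makes the success decision unreliable. The cut-off of three at every N from 6 to 11 does not support that. Nor can a probability be attached. The 50-for-48 allowance covers the whole original study, and the nausea discontinuation figure in section 4.4 is for single-agent veliparib with no time limit. Neither is an induction drop-out rate.

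**Conclusion.** The concern holds in two parts of unequal weight.

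The main part is the response definition. The plan gives two readings, and they reach opposite decisions whenever fewer than three patients respond at the first scan but three or more do so on maximum response. The smallest case is one late response out of three: 11.6% against 5.5%. This assumes that the bound is one-sided, as the plan's own 3 of 10 requires, and that the earlier four patients remain non-responders under either reading. How likely a late response is cannot be taken from the documents.

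The lesser part is the analysis set. The ITT label, the undefined evaluable restriction and the head count of ten do not fit together, and treated patients who are unscanned or replaced have no counting rule. The reported ORR could be inflated, by 2.7 points in the replacement example, but the decision would rarely change.

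ORR is a secondary, preliminary endpoint and the MTD is already established, so the primary objective is untouched. The wording should still be settled before the ORR analysis.

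**What to change.** In the Study Summary and section 10.3:

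- Limit the maximum-response sentence to clinical benefit rate, or name best response as a secondary summary, so that the ORR success rule uses the first imaging only.
- For ORR, replace the evaluable wording with all mutation-positive patients treated at the MTD, planned N = 10.
- Count a patient with no post-baseline assessment as a non-responder, and say whether an End of Treatment scan before week 8 is the first imaging.
- State whether a patient dosed in induction and then replaced under section 4.10 stays in the ORR denominator. Report ORR with and without such patients, applying the exact-bound rule at the actual N.

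The cost is wording only, with no added patients or visits. The reported ORR may be slightly lower, and if two or more replaced patients are kept in addition to the planned ten, four responses would be needed instead of three.

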1.0 INTRODUCTION – BACKGROUND & RATIONALE

1.1 Significant unmet need in treatment of advanced cancers:

Despite the success of molecularly targeted drugs against the activity of one or more proteins involved in tumorigenesis, these agents only benefit a small proportion of patients. Many tumors do not possess an actionable mutation and have limited therapeutic options for subsequent therapy. The advent of immune checkpoint inhibitors has expanded therapeutic options and produced durable responses among immunogenic tumors. However, response is only seen in a poorly defined subset of patients and many patients are refractory to such treatment or relapse after such therapy. We must investigate ways to increase the number of patients with different histologies that may benefit from immune checkpoint inhibition and extend duration of response through the use of novel combination therapy.

1.2 Synthetic lethality of PARP inhibitors:

Inhibitors of poly (ADP-ribose) polymerases (PARP) have demonstrated the biological concept of synthetic lethality.¹⁻³ Two genes are synthetically lethal if loss of either alone is viable whereas concurrent loss results in cell death.⁴ It has been demonstrated that BRCA1 and BRCA2 dysfunction sensitized cells to PARP inhibition, resulting in genomic instability, cell cycle arrest, and apoptosis.⁵ It is thought that PARP inhibitors utilize the homologous recombination⁶ deficiency in BRCA-deficient cells to cause an increase in persistent single strand breaks (SSBs), resulting in collapsed replication forks and ultimately creating double strand breaks (DSB).^{2,7} HR-deficient cells are unable to maintain the integrity of the genome and become nonviable. PARP inhibitors have now demonstrated efficacy for the treatment of ovarian cancer with BRCA mutations.^{8,9} Identification of other mediators of cellular response to PARP inhibitors may reveal additional patient populations that could benefit from this therapeutic approach.

1.3 Tumors with BRCA-like gene defects as a distinct entity:

We have queried a publicly available database (COSMIC) to obtain the overall frequency of mutations of DNA repair genes. We demonstrated that DNA repair genes are mutated at the average frequency of 5% across various tumor types. As with *ALK* rearranged non-small cell lung cancer, these unique subgroup of patients make up a molecularly defined rare group of cancer. It is well known that germ-line mutations in DNA repair pathway genes have been associated with various hereditary cancer syndromes. BRCA 1/2 mutated hereditary breast and ovarian cancer syndrome is a prime example.

There are a number of solid tumors that harbor defects in homologous recombination repair outside of BRCA 1/2 that are referred to as “BRCA-like” tumors or possessing “BRCAness.”¹⁰ Loss or disruption of proteins necessary for HR such as *RAD51*, *ATM*, *ATR*, *CHK1*, *CHK2*, *FANCD2*, and *FANCA* are observed in a variety of tumors. In muscle-invasive bladder cancer, patients with tumors with mutations in DNA repair genes such as *ATM*, *ERCC2*, *FANCD2*, *PALB2*, *BRCA1*, or *BRCA2* demonstrated better survival outcome after cystectomy compared to patients with tumors without mutations. In pancreatic cancer, genomic instability co-segregated with inactivation of DNA repair genes including *ATM*, *BRCA1*, *BRCA2* or *PALB2*. The individuals with defects in these DNA repair mechanisms demonstrated better treatment responses. These observations suggest that somatic mutations in HR DNA repair pathway genes may form a distinct entity across different histologies.

Recently it has been shown that BRCA1/2-mutated tumors were associated with significantly higher CD8+/CD4+ ratio of tumor infiltrating lymphocytes (TILs) and significantly higher peritumoral T cells. These findings support an additional mechanism for the improved survival of patients with BRCA1/2-mutated ovarian cancers in addition to increased sensitivity to platinum chemotherapy¹¹.

1.4 Rationale of PARP inhibitors in BRCA like tumors:

It is expected that tumors displaying inherent or acquired DNA repair defects would most likely respond to PARP inhibition¹². Ongoing research suggests HR deficiency, rather than a specific mutation in the BRCA genes, may be the main driver of cytotoxicity of PARP inhibition.¹³ The BRCA-like behavior has been described based on clinical and molecular features that parallel germline BRCA mutation-associated cancer characteristics. The major clinical BRCA-like behavior identified is susceptibility to platinum compounds and other DNA-damaging agents.^{14,15}

Recent trial (ARIEL2) in ovarian cancer demonstrated that a use of PARP inhibitor (rucaparib) was associated with higher PFS rates among patients with BRCA mutations and BRCA-like wild-type ovarian cancer compared to biomarker-negative tumors. The median PFS for mutation carriers was not reached after 9.4 months, compared with 7.1 months for patients with BRCA-like tumors and 3.7 months for participants who were biomarker negative¹⁶. There are also ongoing efforts to develop a predictive genomic companion diagnostics of HR deficiency that can help determine potential patients who would benefit from PARP inhibitor treatment.

1.5 Overall somatic mutation burden of tumor and defects in DNA repair mechanisms:

Mutations in critical genes such as those involved in DNA repair will likely result in genomic instability and subsequent hypermutability. For example, it is well known that mismatch repair (MMR) deficient tumors have extremely high mutation rates. Similarly, in muscle-invasive bladder cancer, mutations in either of the DNA repair genes (ATM, ERCC2, FANCD2, PALB2, BRCA1, or BRCA2) were associated with higher somatic mutation burden as measured by non-synonymous single nucleotide variant (SNV) and higher T cell clonality as measured by lower T cell receptor (TCR) diversity index. This hypermutable state generated by defects in the DNA repair mechanism may be responsible for altering the tumor 'mutanome', resulting in the production of highly tumor-specific mutated 'neo-antigens', potentially increasing the efficacy of immunotherapies.¹⁷ Tumor infiltrating lymphocytes (TILs) from adoptive cell transfer-treated melanoma patients were found to show specificity for mutated tumor proteins, and further screening to estimate their ability to bind T cell major histocompatibility complex positively correlated with tumor regression. In multiple tumor types, immunogenicity of mutated tumor neo-antigens correlated with patient survival and increased TILs. Patients with MMR deficient colorectal cancer as well as MMR deficient non-colorectal cancers treated with PD-1 inhibitors have demonstrated better response compared with patients MMR proficient tumors. Furthermore, in ovarian cancer and triple negative breast cancer (TNBC) where BRCA1 or 2 mutations are more prevalent than other subtypes, favorable responses to immune checkpoint inhibitors have also been reported.

